4.3. Other Efficacy Endpoints

- Mean percentage changes from baseline in supplemental oral calcium and supplemental calcitriol dosages at each visit
- Proportion of subjects achieving the three conditions of the efficacy endpoint defined above at each visit
- Mean change from baseline in 24-hour urine calcium excretion
- Impact of calcium source (carbonate vs. citrate) on response
- Impact of calcium-sparing diuretics on serum and urinary calcium
- Proportion of subjects that maintain a calcium phosphate product in the range of 35 to 55 mg^2/dL^2
- Distribution of subjects by rhPTH[1-84] doses at the End of Treatment Visit
- Change from baseline in bone turnover markers, bone-specific alkaline phosphatase, serum carboxy-terminal telopeptide of type I collagen, serum procollagen type I amino-terminal propeptide, osteocalcin, PTH antibodies, and BMD by DXA
- Additional subgroup analyses that are specified in the SAP

4.4. Exploratory Endpoints

There is no exploratory endpoint specified for this study.

4.5. Safety Endpoints

The safety endpoints include:

- Adverse events and serious adverse events
- Incidence of adverse events of hypocalcemia (eg, paresthesia, numbness, tetany) and hypercalcemia (eg, constipation, nausea, poor appetite or vomiting, frequent urination, thirst, and kidney stones)
- Incidence of hypercalciuria
- Laboratory test results
 - Hematology (hematocrit, hemoglobin, white blood cells, red blood cells, platelets, differential)

- Serum chemistries (standard Chem-20 panel, including calcium, phosphorus, and albumin)
 - Serum 25-hydroxyvitamin D levels
 - Serum 1,25-dihydroxyvitamin D levels
 - Creatinine clearance
 - Serum bone turnover markers
 - Urinalysis
 - 24-hour urine calcium, phosphate, sodium, and creatinine excretion
 - PTH and *E. coli* protein (ECP) antibodies
- Bone mineral density (BMD) by dual-energy x-ray absorptiometry (DXA)
- Electrocardiogram (ECG) parameters
- Physical examinations (including vital signs)
- Reason for termination from the study

5. Statistical Methods

5.1. General Methodology

All statistical procedures will be completed using SAS version 9.4¹. No formal statistical testing will be conducted for this study. Summary statistics will be provided.

Continuous variables, including those assessed on a discrete scale, will be summarized using descriptive statistics including number of subjects, mean, median, standard deviation, maximum, and minimum. For categorical variables, statistical summaries will include number of subjects and percentages.

For summary purposes, baseline will be defined as the last available pre-dose value, unless otherwise specified. End of treatment (EOT) time point, defined as the last determination of response or last available measurement during the treatment period (from the date of first dose to the date of last dose + 1 day), will be analyzed in addition to the scheduled visits. Visits will be summarized based on the analysis visit windows.

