### **5.3.2 Selection and Timing of Dose for Each Subject**

Subjects will self-administer rhPTH[1-84] in the morning, using the multidose pen injector devices. On the days of clinic visits, the injections of study drug will occur after the serum is taken for laboratory assessments and may be administered by the clinic study personnel.

Calcium and/or vitamin D should be taken in the morning as normal after the rhPTH[1-84] injection.

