## 6.4 Description of Study Procedures

### 6.4.1 Visit 1 Baseline Procedures

RELAY study Week 8 procedures must be performed prior to any baseline procedures. Subjects must sign an ICF for this study prior to having any study-related procedures performed. Additionally, REPLACE completers, who did not participate in the RELAY study, will have to undergo ALL Visit 1 procedures.

Subjects will be instructed to come into the study center after having fasted for approximately 6 to 8 hours. Appointments should be scheduled accordingly to accommodate this fasting status (ie, in the morning). The following procedures will be performed prior to enrollment:

- Update the subject's medical history, demographic information, ongoing concomitant medications, and ongoing AEs from the RELAY/REPLACE study
- Review inclusion/exclusion criteria
- Record all new prescription and nonprescription medications, dietary and nutritional supplements, and vitamins and their doses, frequencies, and durations.
- The occurrence of any new or continuing AE, including episodes of hypocalcemia or hypercalcemia, will be recorded following the signing of the ICF, regardless of whether or not study drug had been administered
- Vital signs measurements (prior to blood draws) and weight
- Physical examination
- 12-lead electrocardiogram
- Blood samples for serum chemistries (including calcium, phosphate, and albumin), hematology, serum 25(OH) vitamin D, creatinine clearance, and bone turnover markers. The

blood sample for serum chemistries will be split and a local total serum calcium will also be performed

- Blood sample for PTH and ECP antibodies
- Urinalysis and 24-hour urine calcium, phosphate, sodium, and creatinine
- Serum  $\beta$ -HCG pregnancy test (WOCBP only)
- Urine pregnancy test for immediate confirmation of non-pregnant status (WOCBP only)
- A BMD test by DXA (omit if subject had a scan performed within the past 6 months in either RELAY or REPLACE studies)
- An FSH test to confirm postmenopausal status, EXCEPT if subjects have met the definition of postmenopausal after the beginning the RELAY/REPLACE study (for newly postmenopausal females only)
- The first dose of study medication will be administered after appropriate fasting laboratory evaluations have been taken
- Subjects will be provided with the following study supplies:
  - Study medication cartridges in sufficient number to supply daily doses until the next scheduled clinic visit
  - Two pen injectors

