5.3.2. Definition of Baseline

For all data including baseline variables, efficacy endpoints, and safety endpoints, the baseline values are defined as follow:

- For subjects who previously completed the REPLACE and RELAY studies or completed only the REPLACE study, the baseline value of REPLACE study will be used as the baseline value for this study;
- For subjects who previously only completed RELAY study, the baseline value of RELAY study will be used as the baseline value for this study;
- For subjects who enrolled in REPLACE and dropped out during optimization and subjects who are new to the rhPTH[1-84] treatment, Visit 1 (BL visit) record of this study will be used as the baseline value.

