6.3. Analysis Populations

The analysis populations to be used in this study are the Safety Population and the Intent-to-Treat (ITT) Population.

The Safety Population includes all subjects who received at least one dose of study drug with any follow-up information. All safety analyses will be conducted on this population.

The ITT population includes all subjects who received at least one dose of study drug and had at least one efficacy measurement. The primary and secondary efficacy analyses will be based on the ITT population.

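### The SAP's end-of-treatment window opens on the day of first dose, so an early leaver's EOT safety result can be a Visit 1 value taken before the first RACE dose

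*SAP*

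**What the plan says.** SAP 5.1 takes EOT as the "last available measurement during the treatment period (from the date of first dose to the date of last dose + 1 day". The rule works by date and has no post-dose condition. EOT "will be analyzed in addition to the scheduled visits", so it does not inherit the limits of the visit windows in SAP Table 5.1, whose first post-baseline window (Week 4) opens on Day 2.

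Protocol 6.4.1 says of Visit 1: "The first dose of study medication will be administered after appropriate fasting laboratory evaluations have been taken". Protocol 5.3.2 gives the same order for clinic days in general: "the injections of study drug will occur after the serum is taken for laboratory assessments".

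The default in SAP 5.1 is that "baseline will be defined as the last available pre-dose value, unless otherwise specified", but SAP 5.3.2 does specify otherwise. For REPLACE completers, with or without RELAY, "the baseline value of REPLACE study will be used as the baseline value for this study". For subjects who completed RELAY only, "the baseline value of RELAY study will be used as the baseline value for this study".

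EOT feeds the laboratory shift tables (SAP 6.8.2), the antibody table (SAP 6.8.4.5) and responder status (SAP 6.7.1).

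**The concern.** A reader takes an EOT row to show where subjects stood at the end of RACE treatment. Under the rule as written, a Day 1 sample taken before the first RACE injection lies inside the EOT window. One would expect the baseline label to keep it out, but for roll-over subjects that label sits on a value from the earlier study. Protocol inclusion criterion 2 requires completion of RELAY or REPLACE, so this should cover nearly everyone.

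Safety is the primary objective, and the exposed subjects are those who leave early. Dosing can stop some days before the termination visit. The protocol allows the End of Treatment visit a window of ± 1 week (Table 6-3), whereas the SAP closes the EOT window at last dose + 1 day. A termination result obtained on Day 203 after a last dose on Day 200 is then discarded, and the pre-dose Day 1 result is reported in its place.

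**Working it through.** The plan has no figure to reproduce: there is no formal testing, and the sample size is a roll-over count. The check applies the stated window to the protocol's schedule.

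**Inputs**
- Window: SAP 5.1. With L the study day of last dose, EOT is the latest measurement on a day d with 1 ≤ d ≤ L + 1.
- Alternative: the same rule with 2 ≤ d ≤ L + 1, the lower bound used in SAP Table 5.1.
- First scheduled repeat after Visit 1 (Protocol 6.2.3 and Table 6-1; target day = 7 × week + 1): central calcium and vital signs Day 29; bone markers Day 57; 24-hour urine and creatinine clearance Day 113; antibodies Day 169; ECG, hematology, full Chem-20 and urinalysis Day 365.
- N about 50 (SAP 3.3).

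**Worked cases** (Visit 1 sample dated Day 1)

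| Last dose | Termination visit | Variable | EOT as written | EOT from Day 2 |
|---|---|---|---|---|
| Day 20 | none | central calcium | Day 1 | missing |
| Day 100 | Day 103 | 24-hour urine, creatinine clearance, antibodies | Day 1 | missing |
| Day 100 | Day 103 | central calcium, bone markers | Day 57 | Day 57 |
| Day 200 | Day 203 | ECG, hematology, Chem-20, urinalysis | Day 1 | missing |
| Day 200 | Day 203 | antibodies | Day 169 | Day 169 |
| Day 200 | Day 201 | all of these | Day 201 | Day 201 |

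The two rules differ only where no post-dose value lies in the window. Any subject with one such value has the same EOT under both.

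**Part of Year 1 with no scheduled post-dose value yet**, (first repeat day − 1) / 364:
- calcium and vital signs: 28/364 = 7.7%
- bone markers: 56/364 = 15.4%
- 24-hour urine and creatinine clearance: 112/364 = 30.8%
- antibodies: 168/364 = 46.2%
- ECG, hematology, Chem-20 and urinalysis: 364/364 = 100%

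These are spans of time, not proportions of subjects. They show which tests are open to the problem and for how long.

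**Weight of one subject:** 1/50 = 2 percentage points. The documents give no dropout rate. If 1 to 5 subjects were affected (an assumption), the share of an EOT table would be 1/50 to 5/50, or 2% to 10%.

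**Responder endpoint.** A Visit 1 determination could stand as EOT only if the subject left before any later in-window calcium value, in practice before the Week 4 sample and with no timely termination visit. The supportive diary analysis needs at least 9 diary days (SAP 5.4.1), so it cannot rest on RACE diary data at Day 1. For the primary, prescribed-dose analysis, the result turns on the sentence about early discontinuation in SAP 5.4.1. Read literally, it removes early leavers from the post-baseline prescribed dose, and the route closes. Read as excluding only the dose prescribed at the termination visit, it leaves the route open.

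**The case against.** The strongest reply is that the protocol already prevents most cases. Protocol 4.4 asks for the end-of-study examinations in non-completers as far as possible. Protocol 6.4.6 includes ECG, hematology, chemistry and urinalysis at the termination visit and places the last dose at that visit, after sampling. When this is followed, the termination values fall inside the window and EOT is correct. That stands: the problem needs both an early exit and no in-window post-dose value.

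Nor does every Visit 1 test fall on Day 1. DXA is omitted if a scan was done in an earlier study within 6 months (Protocol 6.2.7), final RELAY results may be reused (Protocol 6.2.3), and a sample dated before the first dose is already outside the window. Calcium, phosphate and albumin are repeated at every Year 1 visit, so the point on Chem-20 concerns the full panel. These limits also stand.

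Three stronger readings are tempting, and the documents do not support them.
- A reader might infer that changes at EOT are biased towards zero. That would follow if Visit 1 were the baseline. With baseline from REPLACE or RELAY, the substituted row shows change between that baseline and RACE entry, which may be large or small in either direction.
- A reader might call the substituted value untreated. It precedes only the first RACE dose; a RELAY completer has already had 8 weeks of active therapy.
- A reader might infer that early leavers are readily counted as responders, because "The ITT population includes all subjects who received at least one dose of study drug and had at least one efficacy measurement" and that measurement need not be post-dose. The narrow timing and SAP 5.4.1 make this uncertain, so the ITT wording is no ground for a separate objection here.

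**Conclusion.** The point holds as a defect in a stated rule. For a roll-over subject who leaves in Year 1 with a Visit 1 sample dated Day 1 and no later value by last dose + 1 day, SAP 5.1 selects a result from before the first RACE dose and reports it as end of treatment. That row carries no RACE on-treatment information.

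It matters mainly for ECG, hematology, urinalysis and the full Chem-20 panel throughout Year 1, and for 24-hour urine and antibodies in subjects who leave before Weeks 16 and 24 respectively. Each affected subject is worth about 2 points at N = 50. How many there will be, and which way the tables would move, cannot be determined from the documents; the set may be empty. Any responder effect depends on which reading of SAP 5.4.1 is meant. The analyses are descriptive, so no test result is at risk. Correction is still worthwhile because safety is the primary objective and the change is almost free.

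**What to change.** In SAP 5.1, define EOT as the last measurement taken after the first RACE dose (study day 2 or later, matching Table 5.1) and up to last dose + 1 day. Report a subject with no such value as missing at EOT for that variable, and show the number missing in each EOT table. The ITT definition can stay as it is, and no rule counting missing subjects as non-responders is needed.

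The cost is one sentence in the SAP, one date condition in programming and slightly smaller EOT denominators. No subject with an in-window post-dose value changes.

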5.2. Adjustments for Covariates

No preselected covariates are selected for adjustments.

5.3. Visit Windows

5.3.1. Analysis Visit Windows

Analysis visit windows are defined in Table 4.

Table 5. 1 Analysis Visit Window Definition (1st 12 Month of Study)

Analysis Visit	Target Study Day	Analysis Visit Window
Baseline	1	See definition in Section 7.3.2
Week 4	29	[2, 42], and \leq last dose day + 1
Week 8	57	[43, 84], and \leq last dose day + 1
Week 16	113	[85, 140], and \leq last dose day + 1
Week 24	169	[141, 196], and \leq last dose day + 1
Week 32	225	[197, 252], and \leq last dose day + 1
Week 40	281	[253, 308], and \leq last dose day + 1
Week 48	337	[309, 350], and \leq last dose day + 1
Week 52	365	\geq 351, and \leq last dose day + 1 or <start date of the extension period

If there are more than one non-missing observations in the same analysis visit window, the following selection rules will be applied sequentially to determine which observation will be used for analysis:

- The observation that is closer to the target day will be used;
- If Observations are equal-distance in days from the target day, the later one based on measurement date and time will be used.

Analysis visit in the Long Term Extension period will be the same as the nominal visit in the CRF database. No derivation is necessary.

5.3.2. Definition of Baseline

For all data including baseline variables, efficacy endpoints, and safety endpoints, the baseline values are defined as follow:

- For subjects who previously completed the REPLACE and RELAY studies or completed only the REPLACE study, the baseline value of REPLACE study will be used as the baseline value for this study;
- For subjects who previously only completed RELAY study, the baseline value of RELAY study will be used as the baseline value for this study;
- For subjects who enrolled in REPLACE and dropped out during optimization and subjects who are new to the rhPTH[1-84] treatment, Visit 1 (BL visit) record of this study will be used as the baseline value.

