Two-year data show that 100 µg of rhPTH[1-84] is a safe and effective replacement therapy in patients with hypoparathyroidism. Dosing with 100 µg of rhPTH[1-84] QOD resulted in an approximate decrease of 40% in requirements for supplemental calcium and calcitriol. These effects were seen as soon as 1 to 3 months after the onset of rhPTH[1-84] therapy. PTH(1-84) maintained serum calcium within the low normal range. Bone health was an outcome measure for this study and at baseline patients with hypoparathyroidism were reported to have increased cancellous bone volume, and increased trabecular and cortical bone width ([Rubin et al 2008b](#), [Rubin et al. 2008c](#), [Rubin et al. 2008d](#)). Bone turnover was suppressed and bone formation was low. PTH(1-84) therapy QOD led to a marked increase in bone turnover markers, which were accompanied by histopathological changes indicating increased osteoblast activity and alteration in BMD at the spine and radius. PTH(1-84) therapy was well tolerated throughout the 2 years of the study.

A randomized, double-blind, placebo-controlled, phase 3 study in adult subjects with hypoparathyroidism recently concluded (CL1-11-040, REPLACE). This study investigated the effects of daily SC injections of rhPTH[1-84] at doses of 50, 75, or 100 µg administered in the thigh. In addition, a randomized, dose-blinded study investigating fixed doses of rhPTH[1-84] 25 µg and 50 µg in adult subjects with hypoparathyroidism (PAR-C10-007, RELAY) also recently concluded as well as two phase 1 studies. One of the phase 1 studies (C09-002) was a pharmacokinetic/pharmacodynamic study to assess these aspects of rhPTH[1-84] administered at single SC doses of 50 and 100 µg in patients with hypoparathyroidism. The other study (PAR-C10-005) compared the bioequivalence of the Ypsomed and Haselmeier pen injection devices used to administer rhPTH[1-84] in the clinical studies.

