### 4.2 Inclusion Criteria

Subjects who meet all the following inclusion criteria can be enrolled into this study:

1. Signed and dated informed consent form (ICF) before any study-related procedures are performed
2. Previously completed the NPSP558 RELAY study 8 weeks of active therapy and/or previously completed the NPSP558 REPLACE study (Visit 18)
3. Able to perform daily SC self-injections of study medication (or have designee perform injection) via a multidose pen injector into the thigh
4. Willingness and ability to understand and comply with the protocol
5. Women who are: (1) postmenopausal defined as 12 months amenorrhea with appropriate serum follicle stimulating hormone (FSH) levels ( $> 40$  IU/L); (2) surgically sterilized; OR (3) of childbearing potential with a negative pregnancy test at screening and who consent to use two acceptable methods of contraception for the duration of the study, with pregnancy testing at every scheduled visit. Male subjects who have female partners of childbearing potential together also must use 2 acceptable forms of contraception during the subject's participation in the study.
6. Serum creatinine  $< 1.5$  mg/dL at enrollment
7. Total serum calcium  $\leq$  ULN based on local laboratory result prior to enrollment

8. Serum 25(OH) vitamin D  $\leq$  1.5 times the ULN within approximately 16 weeks prior to enrollment

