**Table 6-1 Schedule of Evaluations and Procedures – First 12 Months of Study**

Visit Number	1*	Int.	2	3	4	5	6	7	8	9
Study Procedures / Proposed Study Week a	BL b	1 c	4	8	16	24	32	40	48	52
Visit Windows	± 3 days	± 2 days	± 7 days	± 7 days	± 7 days	± 7 days	± 7 days	± 7 days	± 7 days	± 7 days
Dispense/accountability of calcium/calcitriol supplements (see guideline)	X		X	X	X	X	X	X	X	X
Dispense subject diaries	X									X
Collect used/unused study drug and supplements k			X	X	X	X	X	X	X	X

BL = baseline; DXA = dual-energy x-ray absorptiometry; ECP = *E.coli* protein; FSH = follicle stimulating hormone; GFR = glomerular filtration rate; Int.= interim visit; PTH = parathyroid hormone; WOCBP = women of child-bearing potential

\*Note: Final RELAY study parameters may be used as baseline parameters for this study.

\*\*Any adjustment of study drug or supplemental calcium and calcitriol doses requires testing of total serum calcium concentrations at interim time points.

a Study visits will be conducted at Weeks 1 (baseline), 4, 8, every 8 weeks thereafter through Week 48, and at Weeks 52.

b Week 8 from the RELAY study; subjects will return all used/unused drug, supplements, and pens from RELAY/REPLACE.

c After the End of Treatment visit or early termination visit, subjects who will not continue rhPTH[1-84] treatment will have their total serum calcium and phosphate levels measured 3 to 5 days after the last dose of study medication. Doses of calcium and active vitamin D supplements will be adjusted by the Investigator as appropriate. Thereafter, the Investigator will repeat serum calcium/phosphate monitoring and supplement dose adjustments as appropriate to achieve target serum calcium/phosphate concentrations until the follow up phone call 4 weeks ± 7 days after end of treatment visit. After the 4 week follow up phone call, further management of hypoparathyroidism will occur as part of the subject's long-term non-study medical care.

d Vital signs should be done prior to blood draws.

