## 8.1 Demographic and Baseline Variables

Demographic variables (such as sex, age, race, birthdate, etc.) will be obtained from the REPLACE or RELAY study. Medical history from the RELAY study will be reviewed and updated as necessary. Visit 1 (baseline) for this study (PAR-C10-008, RACE) may be the same day as Visit 4 of the RELAY study. Demographic and/or other variables at baseline will be summarized for medical history, demography, physical examination, vital signs, prior medications, ECG, and laboratory test results.

Prior and concomitant medications will be coded using the World Health Organization Drug Dictionary with regard to drug class and drug name. The number and percentage of subjects with specific prior medications will be summarized. Medical history will be coded using the Medical Dictionary for Regulatory Activities. The number and percentage of subjects with specific histories will be summarized by system organ class and by high-level term and preferred term for each condition.

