3.2.2. Method of Assigning Subjects

Subjects previously enrolled in or who completed the REPLACE or RELAY studies will utilize the same 8-digit subject number that they had been assigned during that study. This number will be utilized to identify the subject throughout the study period. New subjects who were never entered into the REPLACE study will be assigned a new 8-digit subject number.

Subjects will receive study treatment in an open-label fashion at starting doses of rhPTH[1-84] 25 or 50 µg SC QD:

- Subjects with a total serum calcium value of ≤ 9.5 mg/dL will have a starting dose of 50 µg.
- Subjects with a total serum calcium value of > 9.5 mg/dL will have a starting dose as follows:
 - Subjects who are taking supplements (≥ 500 mg oral calcium and/or any calcitriol) will have the supplements reduced or stopped and will start at a dose of 50 µg SC QD.
 - Subjects who are taking minimal or no supplemental calcium (< 500 mg oral calcium) and no calcitriol will have a starting dose of 25 µg SC QD.

The kit number from which cartridges are dispensed to a subject will be recorded on the appropriate eCRF. All subsequent kit numbers will be similarly recorded. All doses of study medication for each subject must be taken from the kit(s) designated for that subject and cartridges from an assigned kit will not be dispensed to any other subject.

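### The third baseline rule in SAP 5.3.2 overlaps the first two with no precedence stated, and for REPLACE optimization dropouts who completed RELAY it selects a value taken after 8 weeks of rhPTH[1-84]

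*SAP*

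**What the plan says.** Entry to RACE is governed by inclusion criterion 2 (Protocol 4.2): "Previously completed the NPSP558 RELAY study 8 weeks of active therapy and/or previously completed the NPSP558 REPLACE study (Visit 18"). There is no other route.

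SAP 5.3.2 sets the baseline for all baseline, efficacy and safety data in three bullets:

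- Bullet 1: "For subjects who previously completed the REPLACE and RELAY studies or completed only the REPLACE study, the baseline value of REPLACE study" is used.
- Bullet 2: "For subjects who previously only completed RELAY study, the baseline value of RELAY study will be used as the baseline value for this study".
- Bullet 3: "For subjects who enrolled in REPLACE and dropped out during optimization and subjects who are new to the rhPTH[1-84] treatment, Visit 1 (BL visit"), meaning that the RACE Visit 1 record is used.

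No order of precedence is given.

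On timing, note b to Protocol Table 6-1 identifies the RACE baseline visit as "Week 8 from the RELAY study", and Protocol 8.1 adds: "Visit 1 (baseline) for this study (PAR-C10-008, RACE) may be the same day as Visit 4 of the RELAY study". On prior exposure, RELAY tested fixed doses of 25 and 50 µg, so every RELAY completer had active drug. REPLACE had a placebo arm: "A randomized, double-blind, placebo-controlled, phase 3 study in adult subjects with hypoparathyroidism recently concluded (CL1-11-040, REPLACE").

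SAP 3.2.2 also provides for entrants outside REPLACE: "New subjects who were never entered into the REPLACE study will be assigned a new 8-digit subject number".

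**The concern.** RACE has no control group, so its efficacy results are responder proportions and changes from baseline. Each subject therefore needs one baseline, fixed in advance. If two bullets apply to the same subject, two programmers can follow the SAP faithfully and produce different results.

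The choice matters most when one candidate is an on-treatment value. Change would then start after part of the drug effect had occurred, and it would be pooled with changes measured from the feeder-study baselines. This touches the percent-reduction conditions for calcium and calcitriol, the serum calcium condition (which also refers to baseline), and the changes in urine calcium, bone markers, BMD, laboratory values and ECG. SAP 5.4.1 also changes its method of deriving the baseline supplement dose according to whether Visit 1 is the baseline.

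**Working it through.** The plan states no figure to reproduce; the sample size was not calculated. The check is an enumeration followed by a small illustration.

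**Step 1: eligible histories.** Take five REPLACE histories (never entered; dropped out during optimization; dropped out later; completed on placebo; completed on active drug) and three RELAY histories (never entered; not completed; completed). That gives 5 × 3 = 15 combinations. Inclusion criterion 2 admits the REPLACE completers (2 × 3 = 6) and the non-completers of REPLACE who completed RELAY (3 × 1 = 3), so 9 are eligible.

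**Step 2: apply the three bullets literally.**

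| Eligible history | Bullet 1 or 2 | Bullet 3 |
|---|---|---|
| REPLACE completed on active, any RELAY history (3) | 1 | no |
| REPLACE completed on placebo, RELAY completed or not completed (2) | 1 | no |
| REPLACE completed on placebo, no RELAY (1) | 1 | yes, as new to rhPTH[1-84] |
| Never in REPLACE, RELAY completed (1) | 2 | no |
| Later REPLACE dropout, RELAY completed (1) | 2 | no |
| REPLACE optimization dropout, RELAY completed (1) | 2 | yes, named in the bullet |

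Bullets 1 and 2 cover 6 + 3 = 9 of 9. Bullet 3 alone covers 0 of 9. Two of 9 histories fall under two bullets; the other 7 have a single baseline. These are counts of histories, not of subjects.

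**Step 3: compare the two candidates in each overlap.**

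- Optimization dropout who completed RELAY: RELAY baseline, or RACE Visit 1 after 8 weeks of rhPTH[1-84]. Protocol 6.4.1 requires the RELAY Week 8 procedures to come first, and the two visits may fall on the same day.
- Placebo completer without RELAY: REPLACE baseline, or RACE Visit 1. Neither follows any rhPTH[1-84]; they differ in timing only.

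**Step 4: look for a tie-break elsewhere.** Protocol 8.3 names both the end-of-study and the baseline values of the earlier studies as RACE baselines and leaves the visits to the SAP. A note to Table 6-1 permits final RELAY values as baseline. SAP 5.1 defaults to the last pre-dose value unless something else is specified, and 5.3.2 does specify something else. None of these settles the overlap.

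**Step 5: illustrate the calcium condition for the first overlap.** Let B be the RELAY baseline dose and f the fractional fall during RELAY. B = 2000 to 3500 mg/day is the typical range given in Protocol 1.2; f = 20% to 40% is assumed. SAP 5.4.1 excludes the dose prescribed at Visit 1 itself, so B(1 − f) stands for the last dose prescribed before that visit, which for someone coming straight from RELAY may already reflect treatment.

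- Cut-off from RELAY baseline: 0.5 × B = 1000 mg (B = 2000) to 1750 mg (B = 3500).
- Cut-off from Visit 1: 0.5 × B × (1 − f). For B = 2000: 800 mg at f = 20%, 600 mg at f = 40%. For B = 3500: 1400 mg and 1050 mg.
- Total fall from B needed to meet the Visit 1 cut-off: 1 − 0.5 × (1 − f) = 60% at f = 20% and 70% at f = 40%, against 50% from the RELAY baseline.

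For B = 2000 and f = 40%, a later dose above 600 mg and up to 1000 mg meets the condition on one baseline and fails it on the other. A dose of 500 mg or less passes on both.

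**Step 6: effect per subject.** 1/50 = 2 percentage points of the responder rate for each subject whose status changes.

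**The case against.** The strongest reply is that the overlap may be empty. Whether RELAY accepted REPLACE optimization dropouts depends on RELAY's eligibility criteria, which these documents do not give. If none entered RACE, that part of bullet 3 has no effect. This stands as a limit on size, but a SAP should not depend on it.

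A second reply is that bullet 3 names that history exactly and so works as a specific exception to bullet 2. The SAP does not say so, and on that reading the on-treatment value would be the planned baseline.

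Third, the protocol contemplates final RELAY values as baseline and delegates the choice to the SAP. That is correct, so an on-treatment baseline does not in itself breach the protocol. It still leaves the SAP to make one choice, and bullets 2 and 3 make opposite ones.

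Fourth, a placebo-arm REPLACE completer falls plainly under bullet 1, which has no arm qualifier, and the words about being new to treatment may have been meant for people outside REPLACE. That is a fair reading, so this overlap is the weaker of the two.

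Fifth, the study's primary objective is safety, its analyses are descriptive, and the calcium (≤ 500 mg) and calcitriol (≤ 0.25 µg) alternatives do not depend on baseline. Titration aims at low supplement doses, so many subjects may qualify through those alternatives. This limits the effect on responder status but not on the change-from-baseline summaries.

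A reader might infer from SAP 3.2.2 that ineligible people were to be enrolled. The sentence does not show that: someone never in REPLACE is eligible after completing RELAY. It is untidy because the same paragraph already has RELAY subjects keep their existing number.

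**Conclusion.** The point holds in a narrow form. Bullets 1 and 2 of SAP 5.3.2 cover every eligible subject, and bullet 3 overlaps them without a stated precedence. The material case is the REPLACE optimization dropout who completed RELAY, for whom bullet 3 sets a baseline after 8 weeks of rhPTH[1-84].

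Three broader inferences are not supported:

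- That eligible subjects in general have two baselines. Seven of the nine eligible histories have one.
- That both overlaps involve a treated baseline. Only one does.
- That the responder rate could shift by a large stated amount. The documents give no count of affected subjects, and it may be small or zero. All that follows is about 2 points per reclassified subject.

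The conclusion assumes that inclusion criterion 2 was applied as written and that dropouts during REPLACE optimization had not received rhPTH[1-84] before RELAY. The documents do not describe that period directly. Nor do they document drug exposure before the RELAY baseline for later REPLACE dropouts, so the RELAY baseline should not be called untreated for everyone under bullet 2.

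**What to change.** Replace the three bullets of SAP 5.3.2 with an exclusive sequence:

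1. Completed REPLACE, either arm, with or without RELAY: REPLACE baseline.
2. Otherwise completed RELAY, including earlier REPLACE dropouts: RELAY baseline.
3. Completed neither: RACE Visit 1, with the subject listed as an eligibility deviation.

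Then align the dependent text. In SAP 5.4.1, limit the Visit 1 dose derivation to the third class. In SAP 3.2.2, delete the sentence on new subjects or state whom it covers. State in the SAP how the rule relates to Protocol 8.3, which names both end-of-study and baseline values, and to the Table 6-1 note allowing final RELAY values as baseline. Report the number of subjects in each class.

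The cost is SAP wording and the matching derivation code. No new data are needed, because the feeder-study baselines are already planned for use.
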